3.5.2 Clinical laboratory values

The summary of laboratory evaluations will be presented for three groups of laboratory tests (Hematology, Serum chemistry and coagulation).

All laboratory values will be converted into SI units and the severity grade calculated using the appropriate common toxicity criteria (CTC).

Descriptive summary statistics (mean, median, standard deviation, minimum and maximum) for the change from baseline to each study visit will be presented. These descriptive summaries will be presented by laboratory test. Change from baseline will only be summarized for patients with both baseline and post baseline values and will be calculated as:

$$\text{change from baseline} = \text{post baseline value} - \text{baseline value}$$

The following summaries will be produced for the laboratory data (by laboratory parameter):

- Number and percentage of patients with worst post-baseline CTC grade (regardless of the baseline status). Each patient will be counted only for the worst grade observed post-baseline.
- Shift tables using CTC grades to compare baseline to the worst post-baseline value will be produced for hematology biochemistry laboratory parameters and coagulation with CTC grades.

- For laboratory parameters where CTC grades are not defined, shift tables to the worst post-baseline value will be produced using the low/normal/high classifications based on laboratory reference ranges.
- A listing of laboratory values will be provided by laboratory parameter. A separate listing will display notable laboratory abnormalities (i.e. newly occurring CTCAE grade 3 or 4 laboratory toxicities)

3.5.3 Vital signs

Analysis of vital sign measurement using descriptive summary statistics (mean, median, standard deviation, min, max) for the change from baseline to worst post-baseline value will be performed. These descriptive summaries will be presented by vital sign. Change from baseline will only be summarized for patients with both baseline and post-baseline values and will be calculated as:

% of change from baseline = [(post-baseline value – baseline value)/ baseline value] x 100;

The change and percent change in body weight from baseline to each assessment time when body weight was measured will be summarized descriptively. Summary will include the mean, standard deviation, median, minimum, and maximum.

Frequency of weight relative change by at least 20% will be summarized.

The number and percentage of patients with clinically notable vital signs changes from baseline will be presented. Clinically notable vital sign results are provided in Table 1-2 below.

Table 1-2 Criteria for clinically notable vital sign abnormalities

Vital sign (unit)	Clinically notable criteria
Weight (kg)	decrease \geq 20% from Baseline increase \geq 20% from Baseline
Systolic blood pressure (mmHg)	≤ 90 and decrease from baseline of ≥ 20 ≥ 180 and increase from baseline of ≥ 20
Diastolic blood pressure (mmHg)	≤ 50 and decrease from baseline of ≥ 15 ≥ 105 and increase from baseline of ≥ 15
Pulse (bpm)	≤ 50 and decrease from baseline of ≥ 15 ≥ 120 and increase from baseline of ≥ 15
Respiratory rate (bpm)	≥ 30 bpm ≤ 10 bpm
Body temperature	$\geq 37.5^{\circ}\text{C}$ $\leq 35^{\circ}\text{C}$

bpm = beats per minute.

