5.2 Inclusion criteria

Patients eligible for inclusion in this study have to meet **all** of the following criteria:

1. Patients must give written informed consent according to local guidelines prior to any screening procedures.
2. Patients must not be eligible for another ongoing INC424 clinical trial.
3. Male or female patients aged ≥ 18 years of age.
4. Patients must be diagnosed with PMF, PPV MF or PET-MF, according to the 2008 revised International Standard Criteria [Appendix I](#), [Swerdlow 2008](#), [Vardiman 2009](#), [Barosi 2008](#)), irrespective of JAK2 mutation status.
5. Patients with PMF requiring therapy must be classified as high risk (3 prognostic factors) OR intermediate risk level 2 (2 prognostic factors, no more), OR intermediate risk level 1 (1 prognostic factor, no more) with an enlarged spleen (assessment to occur at the Screening Visit).

The prognostic factors, defined by the International Working Group ([Cervantes 2009](#)) are:

- Age > 65 years;
- Presence of constitutional symptoms (weight loss, fever, night sweats);
- Marked anemia (Hgb < 10 g/dL)*;
- Leukocytosis (history of WBC $> 25 \times 10^9/L$);
- Circulating blasts $> 1\%$ (in the peripheral blood).

*A Hgb value < 10 g/dL must be demonstrated during the Screening Visit for patients who are not transfusion dependent. Patients receiving regular transfusions of packed

red blood cells will be considered to have Hgb < 10 g/dL for the purpose of evaluation of risk factors.

6. Patients with Intermediate-1 disease and splenomegaly must have a palpable spleen measuring 5 cm or greater from the costal margin to the point of greatest splenic protrusion.
7. Patients must have a peripheral blood blast count percentage of < 10%.
8. Patients with adequate liver function defined as total bilirubin or direct bilirubin $\leq 2.0 \times$ ULN and ALT $\leq 2.5 \times$ ULN.
9. Patients with adequate renal function defined as serum creatinine $\leq 2 \times$ ULN.
10. Patients with an ECOG PS of 0, 1, or 2 ([Appendix IV](#)).
11. Women of childbearing potential must have had a negative serum pregnancy test within 14 days prior to the administration of study drug.
12. Patients must have recovered or stabilized sufficiently from any adverse drug reactions associated with prior treatment before beginning treatment with INC424.

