11.6.3 Other safety data: weight, vital signs, ECG, and death

Weight change from Baseline will be described at each assessment time. Frequency of weight relative change by more than 20% will be summarized. Patients exhibiting clinically notable abnormalities will be listed.

Descriptive statistics and mean change from Baseline will be determined for vital signs (oral temperature, blood pressure and pulse) at each assessment time. Frequency of clinically notable abnormalities will be summarized. Patients exhibiting clinically notable abnormalities will be listed.

Notably abnormal changes in ECG parameters will be displayed in listings.

Deaths reportable as SAEs and non-fatal SAEs will be listed by patient and tabulated by type of AE.

Death rate (any death) at end of study will be summarized, if sufficient number, rate by cause, SOC, and preferred term will also be tabulated, else death and cause will only be listed.

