14.1 Appendix I - Diagnostic criteria for PMF, PPV MF, and PET-MF

Criteria for post-polycythemia vera myelofibrosis (Barosi 2008)	
Required criteria:	
1. Documentation of a previous diagnosis of polycythemia vera as defined by the WHO criteria (Tefferi 2007d) 2. Bone marrow fibrosis grade 2–3 (on 0–3 scale) ³ or grade 3–4 (on 0–4 scale) ^{4,a}	
Additional criteria (two are required):	
1. Anemia ^b or sustained loss of requirement of either phlebotomy (in the absence of cytoreductive therapy) or cytoreductive treatment for erythrocytosis 2. A leukoerythroblastic peripheral blood picture 3. Increasing splenomegaly defined as either an increase in palpable splenomegaly of ≥5 cm (distance of the tip of the spleen from the left costal margin) or the appearance of a newly palpable splenomegaly 4. Development of ≥1 of three constitutional symptoms: >10% weight loss in 6 months, night sweats, unexplained fever (>37.5°C)	
^a Grade 2–3 according to the European classification: ³ diffuse, often coarse fiber network with no evidence of collagenization (negative trichrome stain) or diffuse, coarse fiber network with areas of collagenization (positive trichrome stain). Grade 3–4 according to the standard classification: ⁴ diffuse and dense increase in reticulin with extensive intersections, occasionally with only focal bundles of collagen and/or focal osteosclerosis or diffuse and dense increase in reticulin with extensive intersections with coarse bundles of collagen, often associated with significant osteosclerosis.	
^b Below the reference range for appropriate age, sex, gender and altitude considerations.	

Criteria for post-essential thrombocythemia myelofibrosis (Barosi 2008)	
Required criteria:	
1. Documentation of a previous diagnosis of essential thrombocythemia as defined by the WHO criteria (Tefferi 2007d) 2. Bone marrow fibrosis grade 2–3 (on 0–3 scale) ³ or grade 3–4 (on 0–4 scale) ^{4,a}	
Additional criteria (two are required):	
1. Anemia ^b and a ≥2mg ml ⁻¹ decrease from baseline hemoglobin level 2. A leukoerythroblastic peripheral blood picture 3. Increasing splenomegaly defined as either an increase in palpable splenomegaly of ≥5 cm (distance of the tip of the spleen from the left costal margin) or the appearance of a newly palpable splenomegaly 4. Increased LDH (above reference level) 5. Development of ≥1 of three constitutional symptoms: >10% weight loss in 6 months, night sweats, unexplained fever (> 37.5°C)	

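### SAP Table 1-2 counts body temperature and respiratory rate as notable changes from baseline without any baseline condition, so unchanged or improving patients are included

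*SAP*

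**What the plan says.** SAP 3.5.3 announces the output in these words: "The number and percentage of patients with clinically notable vital signs changes from baseline will be presented". The rules are in Table 1-2, titled "Criteria for clinically notable vital sign abnormalities".

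- Weight: a decrease or increase of at least 20% from baseline.
- Systolic pressure: ≤90 with a fall of at least 20, or ≥180 with a rise of at least 20. The wording that links limit and change is "and decrease from baseline of". Diastolic pressure (≤50 or ≥105, change at least 15) and pulse (≤50 or ≥120, change at least 15) have the same structure.
- Respiratory rate: "≥ 30 bpm ≤ 10 bpm", with nothing further.
- Body temperature: ≥37.5 °C or ≤35 °C, with nothing further.

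The section also says "Change from baseline will only be summarized for patients with both baseline and post-baseline values". That governs who enters the change summaries. It does not require a change in the notable count.

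Protocol 11.6.3 describes the same output as "Frequency of clinically notable abnormalities will be summarized", without mentioning baseline.

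**The concern.** The count is announced as changes from baseline. Four of the six rows deliver that and two do not. For those two, a patient already outside the limit before the first dose is counted as soon as any later value is outside it, whether the value has risen, stayed level or moved towards normal.

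Temperature is where this is likely to matter. Protocol 5.2 lists among the entry prognostic factors "Presence of constitutional symptoms (weight loss, fever, night sweats". Appendix I, for disease that follows polycythemia vera or essential thrombocythemia, includes "night sweats, unexplained fever (>37.5°C", almost the same cut-off as Table 1-2. Protocol 2.1 reports that fever improved with this drug in an earlier phase III trial, so a patient who improves but still reads at or above 37.5 °C is realistic. The study has one arm, so each patient's baseline is the only internal reference, and these two rows do not use it.

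At stake is whether a reader of that one table can tell fever that appeared on drug from fever brought into the study.

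**Working it through.** The plan gives no figure for this count, so there is nothing to reproduce. The check applies Table 1-2 literally to pairs of baseline and post-baseline values.

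| Sign | Baseline → later | Limit met | Change condition | Counted |
|---|---|---|---|---|
| Temperature, °C | 38.2 → 38.2 | yes | none | yes |
| Temperature, °C | 38.5 → 37.6 | yes | none | yes |
| Temperature, °C | 36.8 → 38.2 | yes | none | yes |
| Respiratory rate | 30 → 30 | yes | none | yes |
| Respiratory rate | 34 → 30 | yes | none | yes |
| Respiratory rate | 18 → 30 | yes | none | yes |
| Systolic pressure | 182 → 182 | yes | rise 0 < 20 | no |
| Systolic pressure | 200 → 182 | yes | fall of 18 | no |
| Systolic pressure | 150 → 182 | yes | rise 32 ≥ 20 | yes |
| Pulse | 122 → 122 | yes | rise 0 < 15 | no |
| Pulse | 135 → 122 | yes | fall of 13 | no |
| Pulse | 90 → 122 | yes | rise 32 ≥ 15 | yes |

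Diastolic pressure behaves like pulse: 106 → 106 and 115 → 106 are not counted, 88 → 106 is. The temperature and respiratory-rate rows therefore cannot distinguish stable, improving and newly abnormal patients; the other rows can.

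**Does another part of the plan repair the count?** Other safety domains handle baseline explicitly. Treatment-emergent events must first occur or worsen on treatment (SAP 3.4.1.1). The laboratory worst-grade count openly ignores baseline but is paired with shift tables (SAP 3.5.2). The ECG listing is limited to new or worsening findings (SAP 3.5.4). For vital signs there is no shift table and no exclusion of patients already outside a limit.

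**Size.** The documents do not give the share of patients with a baseline temperature at or above 37.5 °C. For illustration only, assume that share is 1% to 10%, and that 25% to 100% of those patients have at least one later reading at the limit. Protocol 4.1 gives 2238 enrolled.

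- Low end: 2238 × 0.01 × 0.25 = 5.6, about 6 patients.
- High end: 2238 × 0.10 × 1.00 = 223.8, about 224 patients.

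These patients would be counted whether or not they changed. The width of the range shows how little the documents settle.

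**What a baseline condition cannot do.** Take a patient whose true temperature is steady at 37.3 °C, below the limit, with an assumed visit-to-visit SD of 0.3 °C and 10 independent visits (weeks 4, 8, 12 and then every 12 weeks to week 96). The chance that one reading reaches 37.5 °C is P(Z ≥ 0.2/0.3) = 0.2525. The chance of at least one in ten is 1 − 0.7475^10 ≈ 0.945. Requiring the baseline reading to be below 37.5 °C as well gives 0.7475 × 0.945 ≈ 0.71. This is noise over repeated readings, a separate matter that a baseline condition reduces but does not remove.

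**The case against.** The best defence is that this is a wording mismatch. The table title and protocol 11.6.3 both speak of abnormalities, and absolute limits are a legitimate way to count abnormalities. On that view the error is one word in one SAP sentence. This stands in part: relabelling the two rows would remove the contradiction. It would leave a table in which four rows measure change and two do not, with pre-existing fever still mixed into the count.

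The second defence is that the information exists elsewhere. SAP 3.5.3 summarises change from baseline to the worst post-baseline value for each vital sign. Protocol 11.6.3 plans mean change at each assessment, naming temperature, and a listing of patients with notable abnormalities; protocol section 11 lists all analysed data by patient. New fever or infection would be expected mainly among the adverse events. All of this stands and limits the harm. None of it corrects the patient count itself.

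A reader might infer that the trial cannot separate new on-drug fever from disease fever, or that a known slice of the reported rate is pre-existing fever. The documents support neither. The first holds only for this one count. For the second, no baseline temperature distribution is given. Fever is one of three symptoms named within one of five prognostic factors, without a measured reading, and the Appendix I criterion concerns the development of any one of three symptoms in two of the three diagnoses. Exclusion criterion 7 also removes patients with clinically significant infection needing therapy, one source of fever at entry.

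**Conclusion.** The point holds in a limited form. As written, the temperature and respiratory-rate rows count patients whose value was already outside the limit and has not worsened, under a label that says changes from baseline. This follows from the text and needs no assumption about the data, except that the count takes any post-baseline value; the SAP does not name a visit.

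The number affected is unknown. The range of about 6 to 224 patients rests wholly on assumed shares and should not be quoted as an estimate. For respiratory rate the documents give no reason to expect many patients outside the limits at baseline, so the argument there is consistency.

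The consequence is small: one secondary descriptive safety count in a study with no hypothesis tests. The primary analysis already requires events to start or worsen on treatment. Nothing here suggests that the trial's overall safety conclusions are biased.

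**What to change.** In SAP Table 1-2, count body temperature and respiratory rate as notable changes in either of two cases, applied to each limit separately:

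- the limit is met after baseline and was not met at baseline; or
- the limit was already met at baseline and the value moves further in the same direction by an amount the sponsor sets in advance, in parallel with the blood pressure and pulse rows.

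Show patients who met the limit at baseline and did not worsen in a separate row labelled as present at baseline.

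The second case is needed. A rule restricted to newly met limits would drop a patient who goes from 37.6 °C to 40.0 °C, whereas the blood pressure rows do keep such worsening: systolic 185 → 210 meets ≥180 with a rise of 25. Under the proposed rule 38.2 → 38.2 and 38.5 → 37.6 move to the separate row, 36.8 → 38.2 is still counted, and 37.6 → 40.0 is counted if the chosen amount is no more than 2.4 °C.

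The cost is a worsening amount to be chosen for two rows and a small programming change. Vital signs are already collected at screening and baseline, so no new data are needed. The change does not remove visit-to-visit noise in patients near a limit, and a table footnote should say so.

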3.5.4 Electrocardiogram (ECG)

A listing of all newly occurring or worsening abnormalities will be provided, as well as a by-patient listing of all ECG parameters.

3.6 Resource Utilization

Frequency of hospitalization, of emergency room visits, general practitioner, Specialist, urgent care, splenectomy and splenic irradiation will be summarized at end of each quarter (i.e. every three months after start of study medications).

Overall duration and number of hospitalization at the end-of-study will be summarized.

Change in blood transfusion dependency

The proportion of patients who are transfusion dependent as well as the proportion of patients, whose transfusion status (dependent or independent) changed (from dependent to independent or vice versa) , will be tabulated with summary statistics. For the purposes of this assessment

- **Transfusion dependence at baseline** will be defined as patient who received 6 or more units of red blood cell product(s) during the 12 weeks prior to first study drug administration.
- **New onset of transfusion dependence** will be defined as the use of 6 or more units of red blood cell product(s) during any consecutive 12 weeks prior to end of study for patients who were not transfusion dependent at baseline.
- **New transfusion independency** will be defined as no (0) use of red blood cell product(s) during any consecutive 12 weeks prior to end of study for patients who met the definition of transfusion dependence at baseline.
- **Transfusion dependence response:** will be defined as the use of 5 or less units of red blood cell product(s) during any consecutive 12 weeks prior to end of study for patients who were transfusion dependent at baseline.

Patients who were not transfusion-dependent at baseline and who required transfusions during the study, but not during the last 12 weeks of observation, will be considered transfusion independent.

The number and percent of patients who received any blood component transfusions will be summarized by blood component (PRBC (Packed Red Blood Cells), platelets), and visit when the transfusion data were collected.

Prior and concomitant medications, as listed in protocol Appendix IX will be summarized.

Concomitant medication at week 24, as listed in protocol Appendix IX, will be summarized.

3.7 Interim analyses

An interim analysis will be performed to closely monitor safety, and ensure an appropriate risk/benefit ratio in the patient population with low platelet counts, between 50,000 and 100,000/ μ L. In order to adequately assess the risk/benefit ratio, this analysis will also be performed on non-low platelet patients ($\geq 100,000/\mu$ L), which will be further detailed in analysis plan, who will serve as an internal reference population. This interim analysis will take place when 50 patients with low platelets have completed 6 months of treatment.

Analyses may be performed if needed to fulfill regulatory obligations, to comply with post-approval commitments or for publication purposes.

3.8 Data monitoring committee (DMC)

No DMC are planned for this study.

3.9 Sample size and power considerations

This is an expanded access study and thus no sample size and no power computation was performed. Patient will be enrolled until INC424 is commercially available at their sites of 24 months after LPFV. The maximum number of patients that will be treated in this study is up to 2500 and is based on country assessments of the number of potential patients. Actual number of enrolled patients may vary and reflect individual site conditions, which may lead to imbalance between centers, or countries.

3.10 Pharmacokinetic analyses

Not applicable.

3.11 Other topics

3.11.1 Handling of missing data

Patients with missing baseline values where a change from baseline is calculated or when the baseline is used as a covariate will be excluded from the analysis of that variable. Missing values in the QoL will be handled following the instruction of the instruments.

[figure not shown]
3.11.2 Table of Spleen Response and Loss of Response Criteria by IWG MRT criteria

Patients with spleen length at baseline	Response criteria	Loss of response criteria 1
Less than 5 cm	Non evaluable for response	Non evaluable for loss of response
Between 5 and 10 cm	Responder: achieve non palpable spleen	Splenomegaly 5 cm or more
	Stable disease: does not meet criteria for response NOR for disease progression	Meet criteria of progressive disease
	Progressive disease: increase of 100% from baseline	-
More than 10 cm	Responder: reduction of 50%	Loss of the 50% reduction
	Stable disease: does not meet criteria for response NOR for	Meet criteria of progressive disease

[figure not shown]
	disease progression	
	Progressive disease: increase of 50% from baseline	-

3.11.3 Dynamic International Prognostic Scoring System (DIPSS)

The DIPSS can be used to assess a patient's prognosis as conditions change over time.

The risk level is assigned by the total score:

4 Change to protocol specified analyses

The definitions for the transfusion dependence at baseline, new onset of transfusion dependence and new transfusion independency (protocol v05 section 11.6.4.1) are not current. For the final analysis these definition have been updated as per IWG MRT 2013 ([section 3.6](#) of this SAP).

Clinical Study Report

Appendix 16.1.9 Documentation of statistical methods

FACIT-Fatigue Scale questionnaire:

FACIT-Fatigue scale consists of a total of 13 items (an item is equivalent to a question); each item is scored on a scale of 0 to 4. For some questions, a reversal of the raw item score is required to make all item scores in the same direction: higher the score is, better the QOL is. For each raw item score where reversal is required, the reversal will always be calculated by:

$$\text{New Item Score} = 4 - \text{Raw Item Score}$$

Based on the 13 individual item scores, the total score will be derived:

FACIT- Fatigue total score = sum of all the individual scores

FACIT-Fatigue scoring guidelines

Instructions:

1. Record answers in "item response" column. If missing, mark with an X.
2. Perform reversals as indicated, and sum individual items to obtain a score.
3. Derive total score.
4. The higher the score, the better the QOL.

The FACIT-Fatigue Scale questionnaire consists of the following 13 questions.

1. I feel fatigued
2. I feel weak all over
3. I feel listless ("washed out")
4. I feel tired
5. I have trouble starting things because I am tired
6. I have trouble finishing things because I am tired
7. I have energy
8. I am able to do my usual activities
9. I need to sleep during the day
10. I am too tired to eat
11. I need help doing my usual activities
12. I am frustrated by being too tired to do the things I want to do
13. I have to limit my social activity because I am tired

FACT-Lymphoma questionnaire

FACT-Lymphoma questionnaire consists of a total of 42 questions; each question takes an item score of 0 to 4. For some questions, a reversal of the raw item score is required to make all item scores in the same direction: higher the score is, better the QOL is. For each raw item score that the reversal is required, the reversal will always be calculated by

$$\text{New Item Score} = 4 - \text{Raw Item Score}$$

Based on the 42 individual item scores, the following 5 subscales will be derived:

1. **Physical Well-Being (PWB)**: it is the mean of non-missing individual item scores from Questions GP1, GP2, GP3, GP4, GP5, GP6, and GP7 multiplied by 7, where each item score is the reverse of the raw item score.
2. **Social/Family Well-Being (SWB)**: it is the mean of non-missing individual item scores from Questions GS1, GS2, GS3, GS4, GS5, GS6, and GS7 multiplied by 7.
3. **Emotional Well-Being (EWB)**: it is the mean of non-missing individual item scores from Questions GE1, GE2, GE3, GE4, GE5, and GE6 multiplied by 6, where each item score is the reverse of the raw item score except for the 2nd item score from Question GE2.
4. **Functional Well-Being (FWB)**: it is the mean of non-missing individual item scores from Questions GF1, GF2, GF3, GF4, GF5, GF6 and GF7 multiplied by 7.
5. **Lymphoma Subscale (LymS)**: it is the mean of non-missing individual item scores from Questions P2, LEU1, BRM3, ES3, LYM1, LYM2, BMT6, C2, GA1, H18, N3, LEU6, LEU7, BRM9, and LEU4 multiplied by 15, where each item score is the reverse of the raw item score.

A subscale will be missing if the corresponding item scores are all missing. Based on the 5 subscale scores, the following 3 total scores will be calculated:

- FACT-Lymphoma Trial Outcome Index (TOI) = PWB + FWB + LymS
- FACT-G total score = PWB + SWB + EWB + FWB
- FACT-Lymphoma total score = PWB + SWB + EWB + FWB + LymS

A total score will be missing if any of the corresponding subscales is missing.

FACT-Lymphoma scoring guidelines

Instructions:

5. Record answers in "item response" column. If missing, mark with an X.
6. Perform reversals as indicated, and sum individual items to obtain a score.
7. Multiply the sum of the item scores by the number of items in the subscale, then divide by the number of items answered. This produces the subscale score.
8. Add subscale scores to derive total scores (TOI, FACT-G & FACT-Lymphoma).
9. The higher the score, the better the QOL.

Subscale	Item code	Reverse item?	Item response	Item score
PHYSICAL WELL-BEING (PWB) Score range: 0-28	GP1	4	—	= _____
	GP2	4	—	= _____
	GP3	4	—	= _____
	GP4	4	—	= _____
	GP5	4	—	= _____
	GP6	4	—	= _____
	GP7	4	—	= _____

Sum individual item scores: _____

Multiply by 7: _____

Divide by number of items answered: _____ =PWB subscale score

SOCIAL/FAMILY WELL-BEING (SWB) Score range: 0-28	GS1	0	+	_____	= _____
	GS2	0	+	_____	= _____
	GS3	0	+	_____	= _____
	GS4	0	+	_____	= _____
	GS5	0	+	_____	= _____
	GS6	0	+	_____	= _____
	GS7	0	+	_____	= _____

Sum individual item scores: _____

Multiply by 7: _____

Divide by number of items answered: _____ =SWB subscale score

EMOTIONAL WELL-BEING (EWB) Score range: 0-24	GE1	4	—	_____	= _____
	GE2	0	+	_____	= _____
	GE3	4	—	_____	= _____
	GE4	4	—	_____	= _____
	GE5	4	—	_____	= _____
	GE6	4	—	_____	= _____

Sum individual item scores: _____

Multiply by 6: _____

Divide by number of items answered: _____ =EWB subscale score

FUNCTIONAL WELL-BEING (FWB) Score range: 0-28	GF1	0	+	_____	= _____
	GF2	0	+	_____	= _____
	GF3	0	+	_____	= _____
	GF4	0	+	_____	= _____
	GF5	0	+	_____	= _____
	GF6	0	+	_____	= _____
	GF7	0	+	_____	= _____

Sum individual item scores: _____

Multiply by 7: _____

Divide by number of items answered: _____ =FWB subscale score

FACT-Lymphoma scoring guidelines (Version 4) – Page 2

Subscale	Item code	Reverse item?	Item response	Item score
LYMPHOMA SUBSCALE (LYMS) Score range: 0-60	P2	4	–	_____ = _____
	LEU1	4	–	_____ = _____
	BRM3	4	–	_____ = _____
	ES3	4	–	_____ = _____
	LYM1	4	–	_____ = _____
	LYM2	4	–	_____ = _____
	BMT6	4	–	_____ = _____
	C2	4	–	_____ = _____
	GA1	4	–	_____ = _____
	HI8	4	–	_____ = _____
	N3	4	–	_____ = _____
	LEU6	4	–	_____ = _____

Sum individual item scores: _____

Multiply by 15: _____

Divide by number of items answered: _____ =LYM subscale score

To derive a FACT-Lymphoma Trial Outcome Index (TOI):

Score range: 0-116

$$\underline{\hspace{2cm}} + \underline{\hspace{2cm}} + \underline{\hspace{2cm}} = \underline{\hspace{2cm}} = \mathbf{\underline{FACT-Lymphoma\ TOI}}$$

(PWB score) (FWB score) (LymS score)

To derive a FACT-G total score:

Score range: 0-108

$$\underline{\hspace{2cm}} + \underline{\hspace{2cm}} + \underline{\hspace{2cm}} + \underline{\hspace{2cm}} = \underline{\hspace{2cm}} = \mathbf{\underline{FACT-G\ Total}}$$

score

(PWB score) (SWB score) (EWB score) (FWB score)

To derive a FACT-Lymphoma total score:

Score range: 0-168

$$\mathbf{(PWB\ score) + (SWB\ score) + (EWB\ score) + (FWB\ score) + (LymS\ score) = \underline{FACT-Lymphoma\ Total\ score}}$$
